Appendix 2: Statistical Tables – Extension study

Table B 1 - Patients' disposition - extension study

Total (n=xx) Patient agree to be followed for post-treatment evaluations, n (%) No Total Patient agree to be followed for survival, n (%) Yes No Total Primary reason for end of treatment, n (%) Adverse Event(s) Subject withdrew consent Lost to follow-up Administrative problems. Death Disease progression Subject is unable to tolerate the minimum pasireotide LAR dose of 40 mg. Acute or progressive vision loss confirmed by a new visual field evaluation. Uncontrolled diabetes mellitus. Clinically significant abnormal test procedure result(s). Clinically significant abnormal laboratory value(s) Protocol deviation Investigator's decision Other Study populations, n (%) Safety

Table B 2 – Concomitant medication – extension study – FAS population

Table B 2 – Concomitant med	dication – extension study – FAS population	
	Total	
	_(n=xx)	
Any medication or significant nor	ı-drug therapy, n (%)	
Yes		
No		
Total		

Table B 3 – Treatment – extension study – FAS population

	Total (n=xx)					
	V13	V16	V19	V22	V25	Extension phase
Study medication administered, n (%)	-					•
Yes						_
No						_
Total						-
Dose, n (%)						
60 mg						-
40 mg						-
Total						-
Exposure (days) ^{a)}						
N						
Mean						
Median						
Standard Deviation						
Minimum						
Maximum						
Mean administration dose (mg)b)						
N						
Mean						
Median						
Standard Deviation						
Minimum						
Maximum						

a) The difference between the last administration and the first administration of extension phase, in days.
b) Cumulative dose (total dose administered in the extension phase) divided by number administrations (extension phase).

Table B 4 – Magnetic resonance imaging – FAS population

	Total			
	(n=xx)			
	V16	V22	V28	
Volume (cm³)				
N			-	
Mean			-	
Median			-	
Standard Deviation				
Minimum				
Maximum			-	
Tumor is not visible Missing values			-	
iviissing values			-	
Volume change ^{a)} (cm ³)				
N Mean				
Median				
Standard Deviation				
Minimum				
Maximum				
Percentage change in volume ^{a)} (%)				
N				
Mean				
Median				
Standard Deviation				
Minimum				
Maximum				
Reduction of tumor volume ^{b)} , n (%)				
Yes No				
≥20% tumor volume reduction ^{c)} , n (%)				
Yes				
No Total				
Total				
≥20% tumor volume reduction using LOCF method, n (%)				
Yes				
No				
Total				
For patients who achieved a reduction in tumor volume				
of at least 20% with respect to the initial tumor volume				
in the core phase				
≥20% tumor volume reduction ^{c)} , n (%)				
Yes				
No				
Total				
For patients who achieved a reduction in tumor volume				
$$ $\!$ $\!$ $\!$ $\!$ $\!$ $\!$ $\!$ $\!$ $\!$ $\!$				
phase				
≥20% tumor volume reduction ^{c)} , n (%)				
Yes				
No				
Total				

a) The difference between visit i and V1.

b) For reduction='yes' will be considered all patients who obtained 'volume in visit i – volume in V1' >0.
c) For reduction ≥20%='yes' will be considered all patients who obtained 'Percentage change in volume at visit i' ≥20.

Table R 5 - Disease-related symptoms - FAS population

	Total					
	(n=xx) V13	V16	V19	V22	V25	V28
Headache, n (%)						
Absent						
Mild						
Moderate						
Severe						
Very severe						
Total						
mproved, n (%)						
Yes						
No						
Total						
Visual disturbances, n (%)						
Absent						
Mild						
Moderate						
Severe						
Very severe						
Total						
mproved, n (%)						
Yes						
No						
Total						
Fatigue, n (%)						
Absent						
Mild						
Moderate						
Severe						
Very severe						
Total						
mproved, n (%)						
Yes						
No Tatal						
Total						
Erectile dysfunction, n (%)						
Yes						
No						
Total						

Improved, n (%)

Yes

No

Total

Regular menses, n (%)

Yes

No

Total

Improved, n (%)

Yes

No

Total

a) For each symptom, it will considered as improvement if the severity reduce at least one point (eg. 'Severe' at v1 and 'moderate' at v1 will be considered as improvement in vi).

b) For patients who registered 'No' in V_1 and 'Yes' in v_i it will be considered as an improvement in v_i . c) For patients who registered 'No' in V_1 and 'Yes' in v_i it will be considered as an improvement in v_i .

Total (n=xx)	Table B 6 – Alpha-su	ubunit – FAS popula	ation		
α subunit (ng/mL) - N - Mean - Median - Standard Deviation - Minimum - Maximum - Normal - Abnormal - CS - NCS - Reduction of α subunit ≥50% ^{b)} , n (%) Yes - No - Total -					
N Mean		V16	V22	V28	
N Mean					
N Mean					
N Mean					
N Mean					
N Mean					
N Mean					
N Mean					
N Mean					
N Mean					
N Mean					
N Mean					
N Mean					
N Mean					
Mean - Median - Standard Deviation - Minimum - Maximum - Normal - Abnormal - CS - NCS - Reduction of α subunit ≥50%b), n (%) - Yes - No - Total -	N SUBURIT (ng/mL)		-		
Standard Deviation Minimum Maximum Normal Abnormal CS NCS Reduction of α subunit ≥50%b), n (%) Yes No Total	Mean		-		
Minimum - Maximum - Normal - Abnormal - CS - NCS - Reduction of α subunit ≥50% ^{b)} , n (%) - Yes - No - Total -			-		
Maximum - Normal - Abnormal - CS - NCS - Reduction of α subunit ≥50%b), n (%) Yes - No - Total -			-		
Abnormal - CS - NCS - Reduction of α subunit ≥50% ^{b)} , n (%) Yes - No - Total - CS - Total - - - - - - - - - - - - -			-		
Abnormal - CS - NCS - Reduction of α subunit ≥50% ^{b)} , n (%) Yes - No - Total - CS - Total - - - - - - - - - - - - -	Normal		_		
CS NCS - Reduction of α subunit ≥50% ^{b)} , n (%) Yes No Total - Total - NO - Total - NO - Total - Total - NO - Total - Total - Total - Total			-		
NCS Reduction of α subunit ≥50% ^{b)} , n (%) Yes No Total - - - - - - - - - - - - -			-		
Yes - No - Total -	NCS		-		
Yes - No - Total -	Reduction of α subunit ≥50%b), n (%)				
Total -	Yes		-		
			-		
CC. Clinian III. significants NCC. Net aliminally significant	Total		-		
CN: CHOICAIN SIGNIFICANT: NEN: MOT CHNICAIN SIGNIFICANT	CS: Clinically significant; NCS: Not clinically significant.				

b) For reduction \geq 50%='yes' will be considered all patients who obtained percentage change from baseline in α subunit at visit i' \geq 50.

Table B 7 – Visual field – FAS population

	Total				
	(n=xx)				
	V16	V22	V28		
Right eye					
Normal/abnormal, n (%)					
Normal					
Abnormal					
Mild					
Severe					
Total					
Findings, n (%)					
Upper right quadrantanopia					
Upper left quadrantanopia					
Lower right quadrantanopia					
Lower left quadrantanopia					
Temporal hemianopsia					
Nasal hemianopsia					
Other					
Evolutive information, n (%)					
Stable					
Improved					
Worsened					
Total					
Left eye					
Normal/abnormal, n (%)					
Normal					
Abnormal					
Mild					
Severe					
Total					
Findings, n (%)					
Upper right quadrantanopia					
Upper left quadrantanopia					
Lower right quadrantanopia					
Lower left quadrantanopia					
Temporal hemianopsia					
Nasal hemianopsia					
Other					
Evolutive information, n (%)					
Stable					
Improved					
Worsened					
Total					
10001					

Table B 8 – Gallblader ultrasound – FAS population

	Total (n=xx)	
	V16 V28	
Gallblader ultrasound performed, n (%)		
Yes		
No		
Total		
If yes		
Any gallstones detected, n (%)		
Yes		
No		
Total		
Any sludge detected, n (%)		
Yes		
No		
Total		
Dilatation of the intra or extra hepatic ductal sy	tem, n (%)	
Yes		
No		
Total		
Location of dilatation, n (%)		
Intrahepatic ductal system		
Extrahepatic ductal system		
Total		

Table B 9 – Adverse events and serious adverse events in the extension study – Safety population

Total (n=xx) Patients with at least one adverse event, n (%)a) Yes Total Patients with at least one serious adverse event, n (%)a) Yes No Total Grade of adverse events, n (%)b) Grade 1 Grade 2 Grade 3 Grade 4 Total Grade ≥ 3 Relationship of study drug, n (%)b) Not suspected Suspected Total Action taken for adverse event, n (%)b) No action taken. Study drug dosage adjusted / temporarily interrupted. Study drug permanently discontinued due to this adverse event Concomitant medication taken Non-drug therapy given Hospitalization / prolonged hospitalization Serious adverse events, n (%)b) Yes No

a) Percentage calculated within the total number of patients of safety population (n=xx).

b) Percentage calculated within the total number of adverse events reported by safety population (n=xxx).

Table B 10 – Incidence of adverse events in the extension study – Safety population

	Total (n=xx)	
Incidence of adverse events, n (%)		
Xxxxx		

a) Percentage calculated for total of patients of patients of the safety population (n=xx).

Table B 11 – Incidence of serious adverse events in the extension study – Safety population

	Total (n=xx)	
Incidence of serious adverse events, n (%)		
Xxxxx		

a) Percentage calculated for total of patients of patients of the safety population (n=xx).

Table B 12 – Incidence of serious adverse events with suspected relationship with study drug in the extension study – Safety population

	Total (n=xx)
Incidence of adverse events with suspected relationship with study	
drug, n (%)	
Xxxxx	

a) Percentage calculated for total of patients of patients of the safety population (n=xx).

Table B 13 – Incidence of serious adverse events with suspected relationship with study drug in the extension study – Safety population

	Total (n=xx)
Incidence of serious adverse events with suspected relationship with study drug, n (%)	
Xxxxx	

a) Percentage calculated for total of patients of patients of the safety population (n=xx).

Table B 14 – Adverse events in the extension study – Safety population

	Total (n=xx)	
Adverse events, n (%)		
Xxxxx		

Percentage calculated within the total number of adverse events reported by safety population (n=xxxx).

Table B 15 – Serious adverse events in the extension study – Safety population

	Total (n=xx)
Serious adverse events, n (%)	
Xxxxx	

Percentage calculated within the total number of serious adverse events reported by safety population (n=xxxx).

Table B 16 – Adverse events with suspected relationship with study drug in the extension study – Safety population

	Total (n=xx)	
Adverse events with suspected relationsh	ip with study drug, n (%)	
Xxxxx		

Percentage calculated within the total number of adverse events with remote, possible or probable relationship with study drug reported by safety population (n=xxxx).

Table B 17 – Serious adverse events with suspected relationship with study drug in the extension study – Safety population

	Total (n=xx)
Serious adverse events with suspected relationship with study drug, n (%)	
Xxxxx Xxxxx	
Xxxxx Xxxxx	
Xxxxx Xxxxx	
AAAAA	

Percentage calculated within the total number of serious adverse events with remote, possible or probable relationship with study drug reported by safety population (n=xxxx).

Table B 18 – Hematology – Safety population

Fable B 18 – Hematology – Safety population	Total (n=xx)			
	V16	V22	V28	
RBC count ((million/mm³)				
N				
Mean Median				
Standard Deviation				
Minimum				
Maximum				
Normal				
Abnormal				
CS				
NCS				
Hemoglobin (g/dL)				
N Mean				
Median				
Standard Deviation				
Minimum				
Maximum				
Normal				
Abnormal				
CS NCS				
NC3				
Hematocrit (%)				
N Mean				
Median				
Standard Deviation				
Minimum				
Maximum				
Normal				
Abnormal				
CS NCS				
RBC count ((million/mm³)				
N Mean				
Median				
Standard Deviation				
Minimum				
Maximum				
Normal				
Abnormal				
CS NCS				
Hemoglobin (g/dL)				
N Mean				
Median				
Standard Deviation				
Minimum				
Maximum				
Normal				
Abnormal CS				

```
Hematocrit (%)
 Mean
 Median
 Standard Deviation
 Minimum
 Maximum
 Normal
 Abnormal
   CS
   NCS
WBC count (/mm³)
 Ν
 Mean
 Median
 Standard Deviation
 Minimum
 Maximum
 Normal
 Abnormal
   CS
   NCS
Eosinophils (/mm³)
 Ν
 Mean
 Median
 Standard Deviation
 Minimum
 Maximum
 Normal
 Abnormal
    CS
    NCS
Neutrophils total (/mm³)
 Ν
 Mean
 Median
 Standard Deviation
 Minimum
 Maximum
 Normal
 Abnormal
   CS
   NCS
Lymphocytes (/mm³)
 Ν
 Mean
 Median
 Standard Deviation
 Minimum
 Maximum
 Normal
 Abnormal
   CS
   NCS
Monocytes (/mm³)
 Ν
 Mean
 Median
```

```
Standard Deviation
 Minimum
 Maximum
 Normal
 Abnormal
   CS
   NCS
Basophils (/mm³)
 Mean
 Median
 Standard Deviation
 Minimum
 Maximum
 Normal
 Abnormal
   CS
   NCS
Band neutrophils (/mm³)
 Mean
 Median
 Standard Deviation
 Minimum
 Maximum
 Normal
 Abnormal
   CS
   NCS
Platelet count (thousand/mm³)
 Mean
 Median
 Standard Deviation
 Minimum
 Maximum
 Normal
 Abnormal
   CS
   NCS
```

Table B 19 – Coagulation – Safety population

	Total (n=xx)						
	V13	V16	V19	V22	V25	V28	V29
PT (%)							
N							
Mean							
Median							
Standard Deviation							
Minimum Maximum							
Maxilliulli							
Normal							
Abnormal							
CS							
NCS							
Total							
APTT (%)							
N (73)							
Mean							
Median							
Standard Deviation							
Minimum							
Maximum							
Normal							
Abnormal							
CS							
NCS							
Total							

Table B 20 – Urinalysis – Safety population

Table B 20 – Urinalysis – Safety population	Total (n=xx)		
	V16	V22	V28
Specific gravity			
N Mean Median Standard Deviation Minimum Maximum			
Normal Abnormal CS NCS			
PH N Mean Median Standard Deviation Minimum Maximum			
Normal Abnormal CS NCS			
Glucose, n (%) Negative 100 mg/dl or 5 mmol/L 250 (+)mg/dl or 15 mmol/L 500 (++)mg/dl or 30 mmol/L 1000 (+++)mg/dl or 60 mmol/L 2000 (++++) mg/dL or 110 mmol/L Total			
Normal Abnormal CS NCS			
Protein, n (%) Negative Trace 30 (+)mg/dl or 0.3 g/L 100 (++)mg/dl or 1.0 g/L 300 (+++)mg/dl or 3.0 g/L > 2000 (++++) mg/dL or > 20 g/L Total			
Normal Abnormal CS NCS			
Blood, n (%) Negative or 0 ca Cells/μL "Non – Hemolyzed" or 10 ca Cells/μL (Trace) "Hemolyzed" or " Trace" " Small" (+) or 25 ca Cells/μL "Moderate" (++) or 80 ca Cells/μL "Large" (+++) or 200 ca Cells/μL Total			
Normal			

```
Abnormal
         CS
         NCS
Bilirubin, n (%)
       Negative
       "Small " (+)
      "Moderate" (++)
"Large" (+++)
      Total
      Not applicable
       Normal
      Abnormal
         CS
         NCS
Ketones, n (%)
      "Negative"
"Trace" (5 mg/dl) or 0.5 mmol/L
"Small" (15 mg/dl) or 1.5 mmol/L
"Moderate" (40 mg/dl) or 4.0 mmol/L
"Large" (80 mg/dl) or 8.0 mmol/L
"Large" (160 mg/dl) or 16 mmol/L
       Total
      Normal
       Abnormal
         CS
         NCS
Leukocytes, n (%)
Negative or 0 ca Cells/μL
      "Trace" or 15 ca Cells/μL
"Small" (+) or 70 ca Cells/μL
      "Moderate" (+++) or 125 ca Cells/µL
"Large" (+++) or 500 ca Cells/µL
       Total
      Not applicable
       Normal
       Abnormal
         CS
         NCS
```

Table B 21 – Biochemistry – Safety population

Table B 21 – Biochemistry – Safety popula	Total	Total		
	(n=xx)			
	V16	V22	V28	
Urea (mg/dL) N				
Mean				
Median				
Standard Deviation Minimum				
Maximum				
Normal Abnormal				
CS				
NCS				
Creatinine (mg/dL)				
N				
Mean				
Median Standard Deviation				
Minimum				
Maximum				
Normal				
Abnormal				
CS				
NCS				
Uric acid (mg/dL) N				
Mean				
Median				
Standard Deviation				
Minimum Maximum				
Waximum				
Normal				
Abnormal				
CS NCS				
CPK (U/L) N				
Mean				
Median				
Standard Deviation				
Minimum Maximum				
Normal				
Abnormal CS				
NCS				
104 (1/1)				
LDH (U/L) N				
Mean				
Median				
Standard Deviation Minimum				
Maximum				
Normal				
Abnormal				
CS				
NCS				

```
Total protein (mg/dL)
   Mean
   Median
   Standard Deviation
   Minimum
   Maximum
   Normal
   Abnormal
     CS
    NCS
Total cholesterol (mg/dL)
   Ν
   Mean
   Median
   Standard Deviation
   Minimum
   Maximum
   Normal
   Abnormal
    CS
    NCS
Low density lipoprotein (LDL) cholesterol (mg/dL)
   Ν
   Mean
   Median
   Standard Deviation
   Minimum
   Maximum
   Normal
   Abnormal
    CS
     NCS
High-density lipoprotein (HDL) cholesterol (mg/dL)
   Mean
   Median
   Standard Deviation
   Minimum
   Maximum
   Normal
   Abnormal
    CS
    NCS
Triglycerides (mg/dL)
   Ν
   Mean
   Median
   Standard Deviation
   Minimum
   Maximum
   Normal
   Abnormal
     CS
    NCS
Sodium (mEq/L)
   Ν
   Mean
   Median
```

Standard Deviation Minimum Maximum Normal Abnormal CS NCS Potassium (mEq/L) Ν Mean Median Standard Deviation Minimum Maximum Normal Abnormal CS NCS Calcium (mg/dL) Mean Median Standard Deviation Minimum Maximum Normal Abnormal CS NCS Phosphorus (mg/dL) Mean Median Standard Deviation Minimum Maximum Normal Abnormal CS NCS Chloride (mEq/L) Ν Mean Median Standard Deviation Minimum Maximum Normal Abnormal CS NCS B12 Vitamin (pg/) Ν Mean Median Standard Deviation Minimum Maximum Normal

```
Abnormal
    CS
     NCS
Folic acid (ng/mL)
   Mean
   Median
   Standard Deviation
   Minimum
   Maximum
   Normal
   Abnormal
    CS
    NCS
HbA1c (%)
   Ν
   Mean
   Median
   Standard Deviation
   Minimum
   Maximum
   Normal
   Abnormal
    CS
    NCS
Fasting blood insulin (\mu IU/mL))
   Ν
   Mean
   Median
   Standard Deviation
   Minimum
   Maximum
   Normal
   Abnormal
     CS
    NCS
Fasting blood glucose (mg/dL)
   Mean
   Median
   Standard Deviation
   Minimum
   Maximum
   Normal
   Abnormal
     CS
     NCS
```

CS: Clinically significant; NCS: Not clinically significant.

Table B 22 – Tests for liver function – Safety population

Table B 22 — Tests for liver function — Safety po	Total (n=xx)		
	V16	V22	V28
SGOT (U/L)			
N			
Mean Median Standard Deviation Minimum			
Maximum			
Normal Abnormal CS			
NCS			
SGPT (U/L) N			
Mean			
Median Standard Deviation			
Minimum Maximum			
Normal Abnormal			
CS NCS			
Alkaline Phosphatase (U/L)			
N Mean			
Median			
Standard Deviation Minimum			
Maximum			
Normal			
Abnormal CS			
NCS			
y-GT (U/L)			
N Mean			
Median			
Standard Deviation Minimum			
Maximum			
Normal			
Abnormal CS			
NCS			
Total bilirubin (mg/dL) N			
Mean			
Median Standard Deviation			
Minimum			
Maximum			
Normal			
Abnormal CS			
NCS			

```
Direct bilirubin (mg/dL)
   Mean
Median
   Standard Deviation
   Minimum
   Maximum
   Normal
   Abnormal
    CS
    NCS
Indirect bilirubin (mg/dL)
   Ν
   Mean
   Median
   Standard Deviation
   Minimum
   Maximum
   Normal
   Abnormal
    CS
    NCS
Albumin (g/dL)
   Ν
   Mean
   Median
   Standard Deviation
   Minimum
   Maximum
   Normal
   Abnormal
    CS
     NCS
```

CS: Clinically significant; NCS: Not clinically significant.

Table B 23 – Hormonal evaluation – Safety population

Table B 23 – Hormonal evaluation – Safe	Total (n=xx)		
	V16	V22	V28
CII (ng/mi)			
GH (ng/mL) N			
Mean Median Standard Deviation			
Minimum Maximum			
Normal Abnormal CS			
NCS			
IGF-I (ng/mL) N			
Mean Median			
Standard Deviation Minimum Maximum			
Normal Abnormal			
CS NCS			
ACTH (pg/mL) N			
Mean Median Standard Deviation			
Minimum Maximum			
Normal Abnormal			
CS NCS			
Cortisol (µg/dl), for patients without intake of g	glucocorticoid		
Mean Median			
Standard Deviation			
Minimum Maximum			
Normal			
Abnormal CS			
NCS			
LH (mUI/mL) N			
Mean Median			
Standard Deviation			
Minimum Maximum			
Normal Abnormal			
CS			
NCS			

```
FSH (mUI/mL)
   Ν
   Mean
   Median
   Standard Deviation
   Minimum
   Maximum
   Normal
   Abnormal
    CS
    NCS
Testosterone (ng/dl)
   Ν
   Mean
   Median
   Standard Deviation
   Minimum
   Maximum
   Normal
   Abnormal
    CS
    NCS
Estradiol (pg/mL)
   Ν
   Mean
   Median
   Standard Deviation
   Minimum
   Maximum
   Normal
   Abnormal
    CS
    NCS
TSH (μUI/mL)
   Ν
   Mean
   Median
   Standard Deviation
   Minimum
   Maximum
   Normal
   Abnormal
    CS
    NCS
Free T4 (ng/dL)
   Ν
   Mean
   Median
   Standard Deviation
   Minimum
   Maximum
   Normal
   Abnormal
    CS
    NCS
Prolactin (ng/mL)
   Ν
   Mean
   Median
```

Standard Deviation
Minimum
Maximum
Normal
Abnormal
CS
NCS

CS: Clinically significant; NCS: Not clinically significant.

Table B 24 – Vital signs – Safety population

	Total							
	(n=xx)							
-	V13	V16	V19	V22	V25	V28	V29	

Systolic blood pressure (mmHg)

Mean

Median

Standard Deviation

Minimum

Maximum

Diastolic blood pressure (mmHg)

Mean

Median

Standard Deviation

Minimum

Maximum

Heart rate (bpm)

Mean

Median

Standard Deviation

Minimum

Maximum

Temperature (ºC)

Ν

Mean Median

Standard Deviation

Minimum

Maximum

Table B 25 – Physical examination – Safety population

	Total (n=xx)						
	V13	V16	V19	V22	V25	V28	V29
Weight (kg)							
N							
Mean							
Median							
Standard Deviation							
Minimum							
Maximum							
Findings, n (%)							
Normal							
Abnormal							
Skin and nails							
Eves							
Nose and sinuses							
Ears							
Mouth and pharynges							
Head and neck Thorax and lungs							
Breast							
Abdomen							
Lymphatic							
Extremities							
Vascular							
Neurological							

Table B 26 – Eastern cooperative oncology group performance status – Safety population

	Total (n=xx)							
	V13	V16	V19	V22	V25	V28	V29	
ECOG result, n (%)								
0								
1								
2								
3								
4								
5								
Total								

ECOG: Eastern Cooperative Oncology Group.

Table B 27 – Electrocardiogram – Safety population

	Total					
	(n=xx) V13	V16	V19	V22	V25	V28
QTcF (msec)						
N N						
Mean						
Median						
Standard Deviation						
Minimum						
Maximum						
Result, n (%)						
Normal						
Abnormal without clinical						
Abnormal with clinical						
Total						
Consultation with cardiologist to						
confirm abnormal ECG?, n (%)						
Yes						
No						
Total						
If yes, cardiologist confirm QTcF						
interval >480msec, n (%)						
Yes						
No						
Total						
Patient discontinued after						
thorough cardiological						
examination, n (%)						
Yes						
No						
Total

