#### **End of Study (EOS) Visit**

After the Main Phase of the study (first 24 weeks of treatment), patients benefiting from pasireotide LAR treatment will be offered the opportunity to continue to receive pasireotide LAR, based on the physician's evaluation and the patient's wishes.

Patients who participate in the Extension Phase will be treated with pasireotide LAR for up to 92 weeks or approximately 2 years (Table 7-2), or until pasireotide or other effective therapy becomes commercially available, or until clinical benefit is no longer seen (whichever occurs first).

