1.2.1 End-points for secondary objectives

The secondary variables are:

Mean change of tumor volume assessed by pituitary MRI from baseline to Week 4, 12, 24, 48, 72 and
 96.

- Percent change of tumor volume assessed by pituitary MRI from baseline to Week 4, 12, 24, 48, 72 and
 96.
- Proportion of patients achieving tumor volume reduction of at least ≥ 20% after 4, 12, 48, 72 and 96 weeks of treatment.
- Time to treatment response for treatment responders, defined as the time from the date of first injection to the first evaluation the patient achieves tumor volume reduction of at least >20%.
- Change from baseline to Week 4, 12, 24, 48, 72 and 96 in disease-related symptoms scores.
- Incidence of pituitary hormonal dysfunction at baseline and at Weeks 4, 12, 24, 48, 72 and 96.
- Proportion of patients achieving alpha subunit reduction of at least 50% at Weeks 4, 12, 24, 48, 72 and 96.
- Proportion of patients achieving normalization of alpha subunit at Weeks 4, 12, 24, 48, 72 and 96.
- Percentage of CTC (≥3) adverse events during treatment with pasireotide LAR.
- Percentage of patients with at least one adverse event with CTC grade ≥ 3.
- Incidence of all adverse events, incidence of laboratory abnormal values and summary of laboratory assessments.
- For extension phase: among patients who had been considered as responsive (*i.e.*, patients who achieved a reduction in tumor volume of at least 20% with respect to the initial tumor volume), assess the number and proportion of patients that remained responsive during the treatment period of extension phase (according to estimates by magnetic resonance at weeks 48, 72 and 96).
- To assess the percentage of patients who remained with tumor volume stable during the study, *i.e.* patients who maintained tumor volume with variation less than 20% with respect to the basal tumor volume (according to evaluations by magnetic resonance imaging at weeks 24, 48, 72 and 96).
- If applicable, assessing whether there was difference in response between patients using dose of 40 and 60 mg of pasireotide LAR.

2 Study design

This is a prospective, multicenter, open-label, single arm, phase II study to evaluate the efficacy and safety of pasireotide LAR in adult patients with NFPA.

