Eligible patients will receive pasireotide LAR 60 mg every 28 ± 3 days for 24 weeks, during the Core Phase of the study. The study is complimented by an extension. As per treating physician' discretion, patients who have benefited from the treatment with pasireotide LAR can enter an Extension Phase where they will continue to receive pasireotide LAR 60 mg at 4-week (\pm 3 days) intervals for up to 2 years or until pasireotide or other effective therapy becomes commercially available or until clinical benefit is noted (whichever comes first). Dose reductions to 40 mg will be permitted based on safety issues. In case of rapid deterioration of the visual field or sudden visual loss, the patient will be discontinued from the study.

During the Core Phase of the study, visits will be performed every 28±3 days. There will be two extra visits: Visit 3 and Visit 6.

The design of the study and a schematic of the Core Phase and Extension Phase are presented in **Figure 1** and **Figure 2**, respectively.

Figure 1 Schematic of the Pasireotide LAR Study of NFPA: Core Phase

[figure not shown]
[figure not shown]

Figure 2 Schematic of the Pasireotide LAR Study of NFPA: Core Phase

^{*}Details of efficacy and safety evaluation, presented in Table A1.

3 Population

The population for this study is adult patients with a diagnosis of NFPA who have not undergone any prior therapy (treatment-naïve) for the disease. As tumor volume changes are difficult to be evaluated in microadenomas and also because they may be misdiagnosed with incidentalomas, only patients with macroadenomas (≥ 1 cm) will be included. A total of 23 patients in 10-13 centers will be enrolled in this single-arm open-label study.

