5.1 Populations for analysis

Full analysis set (FAS): consists of all patients who successfully completed the screening and have received at least one dose of study medication. FAS will be the primary set for all efficacy analyses.

Safety analysis set: consists of all patients who received at least one dose of study drug and had at least one post-baseline safety assessment.

Note the statement that a patient had no AEs (on the Adverse Event e-CRF) constitutes a safety assessment. The safety set will be used for all safety analyses.

The analyzes presented in this section represent the analyzes that will be used for the Core Phase of the trial. A final analysis will be performed when all patients of Extension Phase completed their last visit and will be reported or as additional clinical study report or as an addendum to the Core Phase of the trial report.

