5.4.3 Handling of missing values/censoring/discontinuations

A patient whose tumor volume assessment at baseline (Visit 1) is missing will not be considered for the efficacy assessments. Only those patients will be considered for analysis for which baseline and at least one post baseline records are reflecting non missing values. All the analysis will be performed with as observed data i.e. the primary analysis (Week 24) will be based on only patients that have both baseline and Week 24 tumor volume assessment.

The analysis of the primary endpoint will be based on observed cases since the patients population is naive (including not having any surgery) and it is expected that 24 weeks of treatment is needed before meaningful effect are assessed.

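### Table B 4 is labelled FAS, but Week 48-96 response would be taken over scanned extension patients selected for benefit, so it can exceed the FAS rate, and its LOCF row has no rule

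*SAP*

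**What the plan says.** SAP 5.1 defines the FAS as the set that "consists of all patients who successfully completed the screening and have received at least one dose of study medication", and adds that "FAS will be the primary set for all efficacy analyses". The planned enrolment is 23.

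SAP section 2 restricts entry to the extension: at the treating physician's discretion, "patients who have benefited from the treatment with pasireotide LAR can enter an Extension Phase". Protocol 7.5.7 schedules the Week 48, 72 and 96 MRIs in that phase only. Protocol 6.4 (End of Study Visit) ends extension treatment after a fixed period, when pasireotide or another effective therapy reaches the market, "or until clinical benefit is no longer seen (whichever occurs first"). SAP section 2 words this last condition without the negative. The two passages must be reconciled, and I work from the protocol's text here.

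On missing data, SAP 5.4.3 states that "All the analysis will be performed with as observed data" and explains this for Week 24 as patients with both a baseline and a Week 24 volume. SAP 5.4.4 defines LOCF for Week 24 only. SAP section 5 says that similar methods apply to the extension as appropriate, and gives no separate extension rule.

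The durability endpoint in SAP 1.2.1 is, among responders, to "assess the number and proportion of patients that remained responsive during the treatment period of extension phase". The shell "Table B 4 – Magnetic resonance imaging – FAS population" has columns V16, V22 and V28, an observed response row, a row "≥20% tumor volume reduction using LOCF method, n" (%), and rows limited to patients defined by their core-phase reduction.

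**The concern.** Entry to the extension depends on judged benefit, and exit can depend on loss of it. An observed-case proportion at Weeks 48 to 96 is therefore taken over a group filtered on something close to the outcome, while the title names a population that includes everyone dosed. A reader of the report would take a percentage headed FAS as a statement about all treated patients.

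Two extension results are affected: response at Weeks 48, 72 and 96, and the proportion of responders who stay responsive. Duration of response is a named objective of the extension. An LOCF row at these visits can assume the answer to that question, because it can count a patient who responded and then left as a responder at Week 96.

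**Working it through.** **The plan's own figures.** The SAP states no figure for Weeks 48 to 96. Its sample-size figures reproduce. With 19 patients and a true rate of 10%, P(X ≥ 2) = 1 − 0.9^19 − 19 × 0.1 × 0.9^18 = 1 − 0.135 − 0.285 = 0.580, stated as 58%. Enrolment is 19 × 1.2 = 22.8, rounded to 23. I use 23 as the FAS size.

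**Who can contribute a value after Week 24.** Non-entrants have no scheduled scan. Entrants who stop have an end-of-extension visit 28 ± 3 days after the last dose (Protocol 6.4.4), and Table 7-2 lists MRI at that visit. No rule assigns this scan to Week 48, 72 or 96.

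**Direction.** Let k be the responders seen at a visit and n the patients scanned, with n ≤ 23. Then k/n ≥ k/23. So the observed rate is never below a FAS rate in which patients without a scan are not counted as responders, and it equals that rate only if all 23 are scanned or k = 0.

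**Illustration A (assumed counts): nothing changes after Week 24.** Four patients respond at Week 24; all enter, are scanned and keep their response.

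| Entrants, all scanned | Observed response, Week 48 | Over the FAS |
|---|---|---|
| 8 | 4/8 = 50.0% | 4/23 = 17.4% |
| 12 | 4/12 = 33.3% | 4/23 = 17.4% |
| 16 | 4/16 = 25.0% | 4/23 = 17.4% |

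If Week 24 is itself an observed-case result over the 19 evaluable patients planned, it is 4/19 = 21.1%. All three observed Week 48 rates are higher, although no tumour has changed. Durability is 4/4 = 100% by every method in this case.

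**Illustration B (assumed counts): some loss.** Four responders are among 12 entrants. By Week 48 one responder has no scan and one has lost response on MRI. Scanned: 12 − 1 = 11. Still responding on a scan: 4 − 1 − 1 = 2.

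| Method | Week 48 response | Remained responsive |
|---|---|---|
| Observed cases | 2/11 = 18.2% | 2/3 = 66.7% |
| LOCF, extension entrants | 3/12 = 25.0% | 3/4 = 75.0% |
| LOCF, all FAS | 3/23 = 13.0% | 3/4 = 75.0% |
| No scan = not shown to respond | 2/23 = 8.7% | 2/4 = 50.0% |

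With the same losses and 8 to 16 entrants, the observed rate runs from 2/7 = 28.6% to 2/15 = 13.3%, against 8.7% of the FAS.

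LOCF restores the unscanned responder, so it never falls below the last row. Whether it lies above or below the observed rate depends on who is imputed: 25.0% over entrants and 13.0% over the FAS, on either side of 18.2%.

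All of this reads footnote c of Table B 4 as intended, a decrease of at least 20%. Taken literally, its sign convention would count growth; that is a separate correction.

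**The case against.** The strongest reply is that the shell does not fix the denominator. It is titled FAS, has a header n and a line for missing values, and SAP 5.4.3 sits under the primary objective and spells out Week 24 only. If the title is taken literally, percentages are over all dosed patients and the enrichment disappears. This stands as a limit on the claim: observed-case use at Weeks 48 to 96 is an inference from 5.4.3 and section 5, though a natural one. It does not remove the need for an instruction, since the title and the rule give different percentages and the SAP does not choose.

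A reader might infer three stronger things that the documents do not support.

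- *That long-term response is overstated.* It can be, relative to a FAS rate that does not credit unscanned patients. Benefit is the physician's judgement, not the 20% criterion, and stopping because a therapy became available need not be failure.
- *That durability tends to 100% by construction.* The endpoint is conditional on responders by definition. The volume-based withdrawal reason in Protocol 6.4.5.1 is confirmed growth above 20%, so a responder who drifts back towards baseline can stay in and be counted as not maintained. Only responders who do not enter, or who leave unscanned, are lost.
- *That LOCF necessarily inflates.* Over the whole FAS it brings in non-entrants' earlier non-response, and the scan at the end-of-extension visit limits stale values where it is done and used.

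It can also be said that the endpoints are on-treatment quantities in a small descriptive study sized without power, so counting every unscanned patient as a failure answers a different question. That is fair, and it is why the FAS row belongs beside the observed row rather than in its place.

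**Conclusion.** The concern holds in a limited form. The stated observed-data rule, applied to visits that only benefit-selected patients reach, can give response rates above the FAS rate and an apparent rise after Week 24 without further shrinkage. With 4 lasting responders and 8 to 16 entrants the gap is 25% to 50% against 17%. Durability can be inflated by the loss of core responders who do not enter or are not scanned: 67% against 50% in the example with losses. The LOCF row is undefined at these visits, and the sign of its effect is open.

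All extension counts are assumptions; the documents give none. The direction is relative to a FAS rate that treats patients without a scan as not shown to respond. The change should be made, but it concerns secondary, descriptive results and leaves the Week 24 primary analysis untouched.

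**What to change.** In Table B 4:

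1. Relabel the observed-case rows 'extension patients with MRI at visit', and show the number of entrants and the number scanned at V16, V22 and V28.
2. Add a response row with all FAS patients as the denominator, counting those without a scan as not shown to respond. Present it as a conservative estimate, because some patients stop for reasons other than failure, such as commercial availability of a therapy.
3. For the remained-responsive proportion, use all core-phase responders as the denominator, and show how many did not enter and how many had no scan.
4. Either define LOCF for Weeks 48 to 96, stating who is imputed and how the end-of-extension scan is used, or drop the row.

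The data are already collected. The cost is a few extra rows and smaller long-term percentages in the report.
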